Repeatability	
A small intra-interobserver study was carried out in 1986 and was presented but not published:
 
Intra-observer study: This study asked two trained ophthalmologists to grade a series of standard slides, showing corneal and conjunctival fluorescein staining, on 2 separate occasions. [note: -this study is only relevant to grading photographic records not patients.]
 
 
 Intra-observer κ for grading photographs of staining, using the Oxford scheme. Two observers.	
 
 	Cornea	Conjunctiva	
 
 Observer 1	0.86	0.69	
 
 Observer 2	0.65	0.83	
 
 
Not that values are in the good to excellent range.
 
Inter-observer study: In this study, the same 2 observers
	Intra-observer κ for grading photographs of staining, using the Oxford scheme. Two observers.				Cornea	Conjunctiva	Observer 1	0.86	0.69	Observer 2	0.65	0.83	Hardman Lea et al. 1986 AER abstract.
Intra-observer κ for grading photographs of staining, using the Oxford scheme. Two observers.														
	Cornea	Conjunctiva												
Observer 1	0.86	0.69												
Observer 2	0.65	0.83												

	graded fluorescein staining (blue exciter; yellow filter) in 13 dry eye patients at an interval within 2-3 weeks. 

Inter-observer κ for grading patients with dry eye, using the Oxford scheme. Two observers. Fluorescein; bengal rose	

Observer 1 v 2	Cornea	Conjunctiva	

Fluorescein	0.88	0.48	

Bengal rose	0.87	0.54	

 It is of interest that observations are in the excellent category for cornea, with either stain and in the fair category for conjunctiva.	Inter-observer κ for grading patients with dry eye, using the Oxford scheme. Two observers. Fluorescein; bengal rose			Observer 1 v 2	Cornea	Conjunctiva	Fluorescein	0.88	0.48	Bengal rose	0.87	0.54	
Inter-observer κ for grading patients with dry eye, using the Oxford scheme. Two observers. Fluorescein; bengal rose														
Observer 1 v 2	Cornea	Conjunctiva												
Fluorescein	0.88	0.48												
Bengal rose	0.87	0.54												
Sensitivity	(true positives) [-]													
Specificity	(100 – false positives) [-]													

Source: See Reference (4).

10.7 Appendix 7: Abbreviations

List of abbreviations

ADC	Antibody-drug conjugate
AE	Adverse event
AESI	Adverse event of special safety interest
ALT	Alanine aminotransferase
AST	Aspartate aminotransferase
C1D1	Cycle 1 day 1
CDL	Clinical Development Leader
CIOMS	Council for International Organizations of Medical Sciences
CFR	Code of federal regulations
CONSORT	Consolidated Standards of Reporting Trials
CRF	Case report form
CTCAE	Common terminology criteria for adverse events
ECG	Electrocardiogram
eCRF	Electronic case report form
e.g.	For example
ETDRS	Early Treatment Diabetic Retinopathy Study
EU	European Union
FSH	Follicle stimulating hormone
FU	Follow-up
GCL	Global Clinical Leader
GCP	Good clinical practice
hCG	Human chorionic gonadotropin
HIPAA	Health Insurance Portability and Accountability Act
HRT	Hormonal replacement therapy
IB	Investigator's brochure
ICF	Informed consent form
ICH	International Council for Harmonization
IEC	Independent Ethics Committee
IgG1	Immunoglobulin G subclass 1
IMP	Investigational medicinal product
IRB	Institutional Review Board
IRR	Infusion-related reactions
IUD	Intrauterine device
IUS	Intrauterine hormone-releasing system
IV	Intravenous
IxRS	Interactive voice/web response system
MedDRA	Medical Dictionary for Regulatory Activities
MTD	Maximum tolerated dose
NA	Not applicable
NCI-CTCAE	National Cancer Institute Common Terminology Criteria for Adverse Events
NIMP	Non-investigational medicinal product
OS	Overall survival
PK	Pharmacokinetics
Q3W	Every 3 weeks
QT	Q wave T wave

QTcB	Corrected QT using Bazett's formula
QTcF	Corrected QT using Fridericia's formula
RBC	Red blood cell
ROS	Rollover study
SAE	Serious adverse event
SAP	Statistical analysis plan
SGOT	Serum glutamic-oxaloacetic transaminase
SGPT	Serum glutamic-pyruvic transaminase
SoA	Schedule of Activities
SOC	Standard of care
SPK	Superficial punctate keratitis
SUSAR	Suspected unexpected serious adverse reactions
TEAE	Treatment-emergent adverse event
TESAE	Treatment-emergent serious adverse event
TOC	Table of contents
US/ USA	United States/ United States of America
WBC	White blood cell
WOCBP	Women of childbearing potential

ADC	Antibody-drug conjugate
AE	Adverse event
AESI	Adverse Events of Special Interest
ALT	Alanine Aminotransferase
AST	Aspartate Aminotransferase
ATC	Anatomical Therapeutic Chemical
BAY 94-9343	Anetumab ravidansine
CI	Confidence interval
CRF	Case Report Form
CSR	Clinical Study Report
CTCAE	Common Terminology Criteria for Adverse Events
ENR	Enrolled analysis set
ICF	Informed consent form
IRR	Infusion-related reaction
KM	Kaplan-Meier
LKAD	Last Known Alive Date
MedDRA	Medical Dictionary for Regulatory Activities
MSLN	Mesothelin
N/A	Not Applicable
NCI	National Cancer Institute
OS	Overall Survival
PT	Preferred Term
RBC	Red Blood Cell
ROS	Rollover study
SAE	Serious adverse event
SAF	Safety analysis set
SAP	Statistical Analysis Plan
TEAE	Treatment-emergent adverse event
TESAE	Treatment-emergent serious adverse event
WBC	White Blood Cell
WHO-DD	World Health Organization Drug Dictionary

1. Introduction

Anetumab ravidansine (BAY 94-9343) is an antibody-drug conjugate (ADC) directed at mesothelin (MSLN) antigens that are expressed in a variety of malignancies and conjugated to a synthetic cytotoxic anticancer agent, maytansine derivative (DM4, BAY 1006640). The purpose of this study is to collect long-term safety information on anetumab ravidansine and to enable participants who received an anetumab ravidansine-containing treatment in any Bayer-sponsored anetumab ravidansine parent study to continue to receive study treatment and/or follow-up at the time of parent study closure.

This statistical analysis plan (SAP) is based on procedures and objectives as described in the clinical study protocol amendment 2, dated 18 JUN 2019.

2. Study Objectives

The primary purpose of this study is to assess the long-term safety of continued anetumab raptansine treatment in patients who were treated with anetumab raptansine in a parent study.

Objectives	Endpoints
Primary	
• Safety	
• Incidence of TEAEs• Incidence of TESAEs• Incidence of drug-related TEAEs and TESAEs
Secondary	
• Survival	
• Overall survival (OS)
Tertiary/Exploratory	
• Tumor response	
• Investigator-determined tumor assessment

3. Study Design

This is an open-label rollover study (ROS) to enable participants who received anetumab raptansine in any applicable Bayer-sponsored anetumab raptansine parent study to continue treatment or follow-up (per current epoch of parent study) at the time of parent study closure.

Participants who discontinue treatment in this study will continue to receive survival follow-up in a long-term follow-up phase. All tumor assessments are at the investigator's discretion and per investigator criteria. Clinic visits occur only during treatment and at the end of treatment safety follow-up visit 30 (+5) days after last treatment. This study has no active follow-up phase other than the safety follow-up visit.

4. General Statistical Considerations

4.1 General Principles

Summary tables will be generated by overall and participant data listings will be generated separately for each parent study. Parent studies include Phase 1 studies 15051, 15834, 17631, 18327, and 18329, and Phase 2 study 15743.

The statistical evaluation will be performed using the SAS software package release 9.4 or higher (SAS Institute Inc., Cary, NC, USA). Data will be analyzed using descriptive statistical methods:

Unless otherwise specified, the following statistics will be presented: For continuous and ordinal data, the number of participants with data available and missing data, mean, standard deviation,

minimum, interquartile range, median, and maximum. For categorical variables, the number of participants and percentage in each category will be generated.

If a subgroup has fewer than 8 participants, summary statistics will not be produced, and the results for the subgroup may be reported entirely with listings.

4.2 Handling of Dropouts

Patients enrolled but not treated in this study will not be included in safety or efficacy summaries. All data available will be reported in safety listings.

4.3 Handling of Missing Data

All missing or partial data will be presented in the participant data listing as they are recorded on the Case Report Form (CRF). Missing data will not be imputed for analyses.

4.4 Interim Analyses and Data Monitoring

No interim analyses are planned. Safety will be monitored on an ongoing basis using clinical data only.

4.5 Data Rules

Duration in months will be calculated as (end date – start date + 1) / 30.4375.

4.6 Validity Review Meeting

At the Validity Review Meeting, participants will be assigned to the relevant analysis sets based on the rules described in Section 5.

5. Analysis Sets

For purposes of statistical analysis, the following analysis sets were defined in the protocol:

Analysis set	Description
Enrolled (ENR)	All participants who signed the informed consent form (ICF)
Safety (SAF)	All participants who take at least 1 dose of study intervention within this rollover study

The enrolled analysis set will be used for study disposition and enrollment, and for listings of safety events. The safety analysis set (SAF) will be used for efficacy and safety summaries.

6. Statistical Methodology

6.1 Population characteristics

Where summarized, population characteristics will be summarized by overall on the SAF.

6.1.1 Disposition

The number of participants in each analysis set will be presented on the enrolled analysis set. The number and percentage of SAF participants who enroll, initiate treatment, discontinue treatment, receive safety follow-up, receive long-term follow-up, and discontinue long-term follow-up will be tabulated, along with reasons for discontinuation. Listings of all discontinued subjects including reasons for discontinuation will be provided by parent study.

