6.1.2 Demographic and Baseline Characteristics

Data listings for all enrolled participants will contain the minimal information collected in this study, including parent study, age at entry into the study, weight, age group, sex, and race. Summary statistics will be reported for the SAF. Summary statistics and a listing of cancer type will be produced.

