6.2 Efficacy**6.2.1 Overall Survival**

Overall survival is defined in the SAF as the time from first treatment in this study until death from any cause. Participants without reported death as of the cut-off date for this study will be censored at their last known alive date. Overall survival data will be listed by overall. Last known alive date will be based on dates of actual participant contact including date of last visit or telephone contact of any kind, last assessment, and last laboratory sample collection date. Censoring rules are described in [Table 6-1](#). Details on last known alive date will be described in programming specifications.

Statistical Analysis Plan

BAY 94-9343/20322

Page: 7 of 10

Table 6-1 Censoring for Overall Survival

Situation	End Date	Censored	Reason for Censoring
Death between first treatment date and the date of analysis / database cut-off date (i.e. there is a death date and this date is before or on the date of analysis / database cut-off date)	Date of Death	No	N/A
Alive at the date of analysis / database cut-off date (i.e. there is a clear assessment that the participant was alive this day, e.g. from information collected on or after the date of analysis / database cut-off date)	Last known alive date (LKAD) prior to database cut-off	Yes	No Death
No information of survival status as of the data cut-off date used for an analysis database (e.g., lost to follow-up)	Last known alive date (LKAD) prior to database cut-off	Yes	No Death and no survival status
Lost to follow-up with no contact information at all after the first treatment date	Date of randomization	Yes	Lost to follow-up after randomization date
If month and/or year are missing for death date	The nearest prior time point: Last known alive date (LKAD) prior to database cut-off	Yes	Missing month and/or year for death date

OS will be summarized using Kaplan-Meier estimates [1]. Medians and 95% Brookmeyer-Crowley confidence intervals [2] with complementary log-log transformation [3] will be reported. The number of participants at risk, number of events, and number of censored participants per month will also be reported.

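### SAP 6.1.1 tabulates disposition on the safety set although SAP Section 5 assigns it to the enrolled set, so consented but undosed participants appear in no row (minor)

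*SAP*

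**What the plan says.** SAP Section 5 defines two sets. The enrolled set is everyone who signed the consent form. The SAF is everyone with at least one dose in the rollover study. It then allocates them: "The enrolled analysis set will be used for study disposition and enrollment, and for listings of safety events". The SAF is kept for efficacy and safety summaries.

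SAP 6.1 sets a different default: "Where summarized, population characteristics will be summarized by overall on the SAF". Within it, 6.1.1 has three parts:

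- Set totals: "The number of participants in each analysis set will be presented on the enrolled analysis set".
- The step-by-step table, with reasons for discontinuation: "The number and percentage of SAF participants who enroll, initiate treatment, discontinue treatment, receive safety follow-up, receive long-term follow-up, and discontinue long-term follow-up".
- Listings: "Listings of all discontinued subjects including reasons for discontinuation will be provided by parent study".

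The design foresees participants who are enrolled but not dosed here. SAP Section 3 describes a study for people "to continue treatment or follow-up (per current epoch of parent study) at the time of parent study closure". Protocol Section 2 and Section 4.1 bring patients already in follow-up into this study for applicable parent studies. Protocol 5.1 allows those whose treatment was permanently interrupted in the parent study to join the follow-up portion. Protocol 5.4 defines screen failures as people who consented but did not go on to enter the study, so under Section 5 they too are in the enrolled set.

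**The concern.** Section 5 and 6.1.1 name different sets for the same table, and a programmer cannot follow both. If 6.1.1 is followed, a table that lists *enroll* and *initiate treatment* as separate steps cannot show any drop between them, because everyone in the SAF has by definition done both.

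The participants who make up that drop are also missing from the later rows. This matters most for long-term follow-up. Someone enrolled only for follow-up would not be counted as entering it or leaving it, and the reason for leaving would not be tabulated. Nor would the table show why other participants were never dosed.

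What is at stake is the account of participant flow. Protocol 5.4 wants screen-failure information for transparent reporting and for regulatory queries. Protocol 10.1.9 plans no publication of this study, so the regulatory purpose is the main one left.

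**Working it through.** There is no planned figure to reproduce. Protocol 9.2 says the number of participants cannot be predicted, and protocol 9.1 plans no hypothesis test. The check follows from the set definitions.

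**Notation.** E = enrolled. D = dosed in this study (the SAF). U = E − D, the undosed. F = direct entrants to follow-up, who are part of U. u = U/E. The documents give no value for any of these.

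**Step 1: the first two rows as written.** Among SAF participants, the count for *enroll* is D and the count for *initiate treatment* is D. With a SAF denominator both are D/D = 100%. With an enrolled denominator both would be D/E. 6.1.1 does not state the denominator, but the two rows are identical either way.

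**Step 2: the same rows on the enrolled set.** *Enroll* is E/E = 100%. *Initiate treatment* is D/E = 1 − u. For assumed u of 0, 5, 10, 25 and 50%, that is 100, 95, 90, 75 and 50%.

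**Step 3: all six rows.**

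| Row | As written (SAF) | On the enrolled set |
|---|---|---|
| Enroll | D | count becomes E; percentage stays 100% |
| Initiate treatment | D | count stays D; percentage becomes 100(1 − u)% |
| Discontinue treatment | dosed only | unchanged, SAF denominator kept |
| Safety follow-up | dosed only | unchanged, SAF denominator kept |
| Enter long-term follow-up | dosed only | adds F, if any |
| Discontinue long-term follow-up | dosed only | adds direct entrants who leave, with reasons |

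As written, the undosed count in 0 of 6 rows. On the enrolled set, up to 4 of 6 rows can change.

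**Step 4: the long-term follow-up row, with assumed numbers.** Take E = 20, U = 5 and D = 15, with 9 of the 15 entering long-term follow-up.

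- As written, on a SAF denominator: 9/15 = 60%.
- Enrolled set, all 5 undosed are direct entrants: (9 + 5)/20 = 14/20 = 70%.
- Enrolled set, all 5 undosed are screen failures: 9/20 = 45%.

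The count moves only if there are direct entrants. Screen failures alone change only the percentage, and only if the denominator is E.

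**Step 5: what survives elsewhere.** The set totals give E and D, hence U = E − D, but as one combined number. The discontinuation listing covers all discontinued subjects, though the SAP does not say whether screen failures count as such. The all-enrolled listing in 6.1.2 is described this way: "Data listings for all enrolled participants will contain the minimal information collected in this study, including parent study, age at entry into the study". The remaining items it names are weight, age group, sex and race. Screen-failure status and route of entry are not named, although the list is not presented as exhaustive.

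**Step 6: estimates.** Safety and efficacy summaries are on the SAF under Section 5. For survival, 6.2.1 says: "Overall survival is defined in the SAF as the time from first treatment in this study until death from any cause". Neither depends on the disposition table.

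**The case against.** The strongest reply is that little is hidden. The first sentence of 6.1.1 already reports both set sizes on the enrolled set, so the fraction dosed can be read a line above the table. This stands. A reader might infer that the report could not show how many consenting participants were dosed; the documents do not support that. A reader might also take the assumed shares in Step 2 as a misstatement of up to 50 percentage points. That is not supported either: the 100% depends on an unstated denominator, the undosed share is an assumption, and the correct ratio is recoverable.

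A second reply is that the SAP handles the untreated by listing. SAP 4.2 keeps enrolled but untreated patients out of safety and efficacy summaries and puts their available data in safety listings, and 6.1 defaults to the SAF. But disposition is neither a safety nor an efficacy summary, and Section 5 assigns it to the enrolled set by name. The set totals meet that assignment only in part.

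Third, SAP Section 3 describes long-term follow-up for participants who stop treatment in this study, and survival is confined to the SAF. SAF-based follow-up rows therefore match the survival population. This is a fair point, and the fix should preserve the match.

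Fourth, the undosed groups are conditional. The protocol speaks of applicable studies, of efforts to obtain consent, and of participants who may be enrolled. There may be none. Neither document promises a tabulated split of the untreated, and protocol 5.4 asks for screen-failure information rather than a particular table. Both points stand. SAP 4.1 would in any case send a subgroup of fewer than 8 to listings.

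**Conclusion.** The conflict is real and the table is wrong as written, at minor severity. Its first two rows cannot differ, and consented but undosed participants are in none of the six. What the summary loses is limited to two things: direct entrants' long-term follow-up entry, discontinuation and reasons, and the reasons why participants were not dosed.

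The identity of the two rows and the omission of the undosed follow from the definitions and need no assumption about numbers. How much the table would change does depend on the undosed share. If everyone who consents is dosed, the SAF and enrolled tables agree. No primary safety or overall survival estimate moves.

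**What to change.** In SAP 6.1.1, replace *SAF participants* with *enrolled participants*, in line with Section 5. Keep SAF denominators for discontinuing treatment and for safety follow-up, and state the denominator for every row. In 6.1, exempt disposition from the SAF default. In the two long-term follow-up rows, show direct entrants separately from treated participants, so that the treated figures still describe the survival population.

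A further split of the untreated into screen failures and direct entrants is optional. It is subject to the fewer-than-8 rule and to route of entry being derivable.

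Changing Section 5 to match 6.1.1 would remove the contradiction, but it would leave the undosed in no row.

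The cost is a few words in 6.1, one sentence in 6.1.1, a revised table shell and a slightly longer table. Screen-failure details are already collected under protocol 5.4. Route of entry is not among the screening items named in protocol 4.1. The recorded parent-study number and participant identifier do not show it by themselves, so separating direct entrants may need linkage to parent-study data. Moving the table to the enrolled set does not depend on that linkage.

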6.1.2 Demographic and Baseline Characteristics

Data listings for all enrolled participants will contain the minimal information collected in this study, including parent study, age at entry into the study, weight, age group, sex, and race. Summary statistics will be reported for the SAF. Summary statistics and a listing of cancer type will be produced.

6.1.3 Concomitant Medication

Concomitant medications are non-study medications used between the first date of treatment and 30 days following the last study treatment in this study.

Concomitant medications will be coded using the most recent World Health Organization Drug Dictionary (WHO-DD) version at the time the study ends and the Anatomical Therapeutic Chemical (ATC) classification system.

Concomitant medication will be reported in the safety analysis set. Listings will be provided by parent study.

6.2 Efficacy**6.2.1 Overall Survival**

Overall survival is defined in the SAF as the time from first treatment in this study until death from any cause. Participants without reported death as of the cut-off date for this study will be censored at their last known alive date. Overall survival data will be listed by overall. Last known alive date will be based on dates of actual participant contact including date of last visit or telephone contact of any kind, last assessment, and last laboratory sample collection date. Censoring rules are described in [Table 6-1](#). Details on last known alive date will be described in programming specifications.

Statistical Analysis Plan

BAY 94-9343/20322

Page: 7 of 10

Table 6-1 Censoring for Overall Survival

Situation	End Date	Censored	Reason for Censoring
Death between first treatment date and the date of analysis / database cut-off date (i.e. there is a death date and this date is before or on the date of analysis / database cut-off date)	Date of Death	No	N/A
Alive at the date of analysis / database cut-off date (i.e. there is a clear assessment that the participant was alive this day, e.g. from information collected on or after the date of analysis / database cut-off date)	Last known alive date (LKAD) prior to database cut-off	Yes	No Death
No information of survival status as of the data cut-off date used for an analysis database (e.g., lost to follow-up)	Last known alive date (LKAD) prior to database cut-off	Yes	No Death and no survival status
Lost to follow-up with no contact information at all after the first treatment date	Date of randomization	Yes	Lost to follow-up after randomization date
If month and/or year are missing for death date	The nearest prior time point: Last known alive date (LKAD) prior to database cut-off	Yes	Missing month and/or year for death date

OS will be summarized using Kaplan-Meier estimates [1]. Medians and 95% Brookmeyer-Crowley confidence intervals [2] with complementary log-log transformation [3] will be reported. The number of participants at risk, number of events, and number of censored participants per month will also be reported.

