6.3.3 Adverse Events

Treatment-emergent AEs (TEAEs)

In this study, treatment-emergent adverse events are defined as adverse events starting or worsening during the treatment period. The treatment period extends from the first date of treatment in this study until the safety follow-up (30 days after the last administration of study treatment).

Coding and grading of TEAEs

TEAEs will be coded using the latest MedDRA version, and toxicity will be graded using NCI-CTCAE v5.0. Corneal epitheliopathy events (classified as corneal disorders) will be graded according to the Bayer Grading System.

Study drug-related AEs

AEs will be reported as study drug-related if they are documented by the investigator as related to any study drug.

AEs of Special Interest (AESIs)

Adverse events of special interest include any corneal epitheliopathy and infusion-related reactions (IRRs).

Reporting of TEAEs

The incidence of TEAEs and TESAEs, as well as drug-related TEAEs and TESAEs will be summarized in descriptive summary tables (number and percentage of participants) by latest MedDRA version SOC and preferred term (PT) and by worst grade for the following:

- Overview of TEAEs
- TEAEs
- TEAEs in descending order of frequency by Preferred Term (PT)
- Study drug-related TEAEs
- Study drug-related TEAEs in descending order of frequency by PT
- TESAEs
- TESAEs in descending order of frequency by PT
- Study drug-related TESAEs
- Study drug-related TESAEs in descending order of frequency by PT
- TE(S)AEs leading to permanent discontinuation
- TE(S)AEs leading to dose interruption

- TE(S)AEs leading to dose reduction
- Overview AEs of special interest

All AEs, TEAEs, TESAEs, and TEAEs leading to discontinuation of study drug will be presented in separate listings. Listings will be provided in all enrolled participants. AEs of special interest will be included in summary tables of AEs and will be presented in data listings.

A summary of deaths during the treatment period and following 30 days after treatment end in this study will be reported for the safety set. A listing of all deaths at any time during the study will be provided in all enrolled participants.

6.3.4 **Laboratory assessments**

The following laboratory parameters will be summarized in all treated participants:

- Hematology: platelet count, red blood cell count (RBC), hemoglobin, hematocrit, white blood cell count (WBC) with differential

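### The overall survival censoring table counts a known death as censored when its month or year is missing, and one row relies on a randomization date that this study does not have

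*SAP*

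**What the plan says.** SAP 6.2.1 gives the endpoint in prose: "Overall survival is defined in the SAF as the time from first treatment in this study until death from any cause". It then says who is censored: "Participants without reported death as of the cut-off date for this study will be censored at their last known alive date". The detailed rules are in Table 6-1. Three rows matter here.

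- **Row 1** counts an event when there is a death date on or before cut-off.
- **Row 4** has the situation "Lost to follow-up with no contact information at all after the first treatment date". Its end date is the date of randomization, and its stated reason is "Lost to follow-up after randomization date".
- **Row 5** has the situation "If month and/or year are missing for death date". It sets Censored to Yes, with the last known alive date (LKAD) as end date.

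Below the table, the SAP adds: "The number of participants at risk, number of events, and number of censored participants per month will also be reported". SAP 4.3 states: "Missing data will not be imputed for analyses". SAP 6.3.3 promises: "A listing of all deaths at any time during the study will be provided in all enrolled participants". Protocol 6.3 says that the study has neither randomization nor blinding.

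**The concern.** A participant who falls under row 5 has a reported death. By the prose that participant has had the event; by the table the participant is a non-event. The programmer cannot satisfy both.

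Kaplan-Meier estimation needs censoring that carries no information about the event. Row 5 is triggered by the event, so that condition fails by construction. The error goes one way: fewer events and higher survival. The monthly event counts fall short by the same deaths. The same participant would be a death in the SAP 6.3.3 listing and censored in the OS analysis.

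There is a related gap. A death date that lacks only its day falls outside row 5, and row 1 needs a date, but SAP 4.3 forbids imputing one. No end date can then be computed.

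Row 4 cannot be programmed as written, because no randomization date exists in this study.

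OS is the only secondary endpoint, and protocol 9.4.1 allows these data to be combined with parent-study data to explore long-term survival, so the error could carry forward.

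**Working it through.** **Text check.** The documents contain no OS figure, sample size or event count to reproduce, so the first check sets the rules side by side.

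| Participant | Prose of 6.2.1 | Table 6-1 |
|---|---|---|
| Death reported, full date | Event | Event (row 1) |
| Death reported, month and/or year missing | Event | Censored at LKAD (row 5) |
| Death reported, only day missing | Event | No computable end date (row 1 with SAP 4.3) |
| No contact after first treatment | Censored | Censored at a date that does not exist (row 4) |

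**Hand example for row 5.** Ten participants die at months 1 to 10. The month-5 death lacks its month, and LKAD is month 4.5.

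- Complete dates: S(5) = 5/10 = 0.50, median 5.0, 10 events.
- Row 5: S stays at 6/10 = 0.60 at month 5. Five remain at risk at month 6, so S(6) = 0.60 × 4/5 = 0.48. The median is 6.0, with 9 events.

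The example puts the affected death at the median, where the effect on the median is largest.

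**Size in large samples, all inputs assumed.** With exponential survival and a share p of deaths censored close to the death date, the estimated hazard is multiplied by (1 − p), so the median becomes M/(1 − p). For M = 12 months, p = 1%, 2%, 5% and 10% gives 12.12, 12.24, 12.63 and 13.33.

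A simulation (N = 4000, 200 replicates, potential follow-up uniform over 12 to 24 months) places LKAD by contact interval. The intervals come from the protocol: 21-day cycles on treatment (1.1) and 3-monthly long-term follow-up (Table 1-1). Mean rise in the Kaplan-Meier median, true median 12 months:

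| Deaths affected | 21-day contacts | 3-month contacts |
|---|---|---|
| 1% | +0.12 | +0.11 |
| 2% | +0.24 | +0.23 |
| 5% | +0.61 | +0.57 |
| 10% | +1.32 | +1.23 |

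Repeat runs agreed to within about 0.03 month. For true medians of 6, 12 and 18 months (follow-up 24 to 36 months for the last), the relative rise is 0.8–1.0%, 1.7–2.0%, 4.3–5.2% and 9.2–11.0% at the four rates.

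**Size in a small study.** With N = 20 and exactly one row-5 death, 12-month survival rises by about 0.025 to 0.027. The sampling standard error is √(0.25/20) = 0.112.

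**Row 4.** With the first treatment date as end date, the SAP 4.5 formula gives an OS time of 1/30.4375 = 0.033 months. The effect on the curve is negligible.

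**Does a partial-date rule do better?** Median OS in months from a simulation with N = 2000, 300 replicates, true median 12, follow-up 12 to 24 months and 3-month contacts. The midpoint rule places the death halfway between LKAD and the next scheduled contact.

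| Scenario | Complete dates | Row 5 | Midpoint | Earliest / latest |
|---|---|---|---|---|
| 5% affected | 11.98 | 12.56 | 11.98 | 11.93 / 12.06 |
| 10% affected | 12.03 | 13.26 | 12.03 | 11.94 / 12.14 |
| 5%, two contacts missed | 12.03 | 12.45 | 11.84 | 11.83 / 12.10 |
| 10%, two contacts missed | 12.05 | 12.95 | 11.62 | 11.61 / 12.16 |

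With contacts on schedule the midpoint rule recovers the complete-date median. With two missed contacts it is early by 0.43 month at 10%, against 0.90 month late for row 5. The earliest and latest dates bracket the complete-date median in each case.

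**The case against.** The best defence is that row 5 is a deliberate convention. The prose does not use the word *only*, and it refers to Table 6-1 for the detailed rules. Row 5 agrees with the ban on imputation in SAP 4.3 and with row 1's demand for a death date. It is visible and carries its own censoring reason, and the death stays in the listing of all deaths. This explains the rule, and it is true that nothing is hidden. It does not make event-triggered censoring valid. Treating a known death as a non-event is also a stronger assumption than placing it in a bounded interval.

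The second objection concerns weight, and much of it stands. The trigger is narrow, and the documents do not support any particular rate. At 1% to 2% the shift is 0.1 to 0.24 months on 12. With N = 20 under the same assumptions, about 13 deaths are expected, so the chance of even one row-5 death is 1 − 0.99^13 = 12% at a 1% rate and 1 − 0.98^13 = 23% at 2%. One such death moves 12-month survival by less than a quarter of its standard error. In the ten-person example, had the affected death been at month 6 or later with LKAD half a month before it, the median would have stayed at 5.0. OS is descriptive, with no hypothesis test (protocol 9.1).

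Third, a death first learned of after cut-off, with month or year missing, may not be classifiable as before or after cut-off. The prose criterion of a death reported as of cut-off largely settles this, but the repaired table should carry it over.

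**Conclusion.** The concern holds. Row 5 conflicts with the SAP's own OS text and biases Kaplan-Meier survival upward whenever it is applied. In large samples the median rises by roughly the percentage of deaths affected: about 1% when 1% are affected and 9% to 11% when 10% are. These figures assume exponential survival, the contact intervals above, and rates that the documents do not give. At a rate of zero there is no effect, and in a small study one such death would be lost in sampling error. Row 4 is a wording error. The primary safety endpoints are unaffected. This should be corrected before database lock, but it does not threaten the study's main purpose.

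**What to change.** **Row 5.** Count every death reported by cut-off, and dated on or before it as far as the date is known, as an event (Censored = No). Pre-specify a partial-date rule. For example, use day 15 if only the day is missing; otherwise use the midpoint between LKAD and the next scheduled contact. Constrain the date by any known month or year, and place it after LKAD and no later than cut-off.

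**SAP 4.3.** Add an exception for partial death dates.

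**Sensitivity analysis.** Repeat the OS analysis with the earliest and the latest possible dates.

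**Row 4.** Replace both references to randomization with the date of first treatment in the rollover study.

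**Row 2, minor.** Say that LKAD is taken on or before cut-off, to match row 1.

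The OS prose needs no change. The cost is a few table cells, one exception and one sensitivity analysis. No new data are needed, since LKAD, the visit schedule and any recorded part of the death date already exist. The drawback is imputation error when contacts are missed, and the sensitivity analysis would show how much that matters.
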